To assess the preliminary efficacy of the Activate program we will examine changes in proximal primary outcomes of goal-setting, coping skill efficacy, and average daily active minutes compared between treatment and control groups at baseline and the 12-week follow-up assessment. We will conduct multilevel models with baseline-residualized gain scores for outcomes to identify the effect size for the treatment program on each of the three primary outcomes. Each model will include the baseline outcome covariate as well as additional disease covariates including diabetes technology use and length of diagnosis. All participants will be used in analyses, with missing data addressed with full information maximum likelihood estimation. A power sensitivity function was generated wherein our pilot study analyses were used to determine expected effect sizes. Anticipated effect sizes based on our pilot work for between group differences in behavior-change skills and average daily active minutes are Cohen's d of 0.4 to 1.2. With 60 participants, we will have 80% power to detect a Cohen's d of .7, 60% power to detect a Cohen's d of .6, at 95% power to detect a Cohen's d of .8. Thus, we will be powered to detect all but the smallest of potentially meaningful effects found in our previous intervention pilot work.

In aim 2, we test the impact of the Activate program on secondary mechanisms of biobehavioral self-regulation systems and glycemic and cardiovascular disease risk outcomes closely linked with type 1 diabetes health disparities. To assess changes in putative mechanisms and secondary outcomes we will use baseline-residualized gain scores in multilevel models to identify the effect size for the treatment program on each of the secondary outcomes assessed for behavior regulation, distress, c-reactive protein, mean and variability in daily blood glucose, and cardiovascular disease risk score. For all analyses missing data will be addressed with full information maximum likelihood estimation. A power sensitivity function was generated wherein our pilot study analyses were used to determine expected effect sizes. Based on our pilot work we anticipate effect sizes from Cohen's d of .4 to .8 and thus with 60 participants, we will again have 80% power to detect a Cohen's d of .7, 60% power to detect a Cohen's d of .6, at 90% power to detect a Cohen's d of .8. We will be powered to detect all but the smallest of potentially meaningful effects found in our pilot work.

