Inclusion of Children: Describe efforts to include children. Inclusion is required unless a clear and compelling rationale shows that inclusion is inappropriate with respect to the health of the subjects or that inclusion is inappropriate for the purpose of the study. If children are included, the description of the plan should include a rationale for selecting or excluding a specific age range of children. When included, the plan must also describe the expertise of the investigative team in working with children, the appropriateness of the available facilities to accommodate children, and the inclusion of a sufficient number of children to contribute to a meaningful analysis relative to the purpose of the study. Provide target accrual for this population. Identify whether children are wards of the state. **If children are excluded** then provide appropriate justification.

We are specifically recruiting 60 adolescents aged 13-17 with type 1 diabetes due to the specific developmental challenges associated with disease management during this developmental period and the importance of this period for reducing future health disparities. We anticipate that 60 adolescents will provide sufficient power for examining effect size changes of the intervention (see analysis section).

Our team is uniquely suited to conduct this work as we have recently developed and tested both neural and self-report measures of learning for adolescents with type 1 diabetes and scalable physical activity interventions for youths. PI [name] is a child clinical health psychologist with over 15 years of training in working with adolescents with type 1 diabetes and other chronic diseases including online intervention research. We have not included children that are wards of the state in this study, this is an exclusion criteria. The challenges children that are wards of the state face around diabetes management make engagement in this intervention implausible.

For protocols including the use of an investigational drug, indicate whether women of childbearing potential have been included and, if not, include appropriate justification.

n/a

If HIV testing is included specifically for research purposes explain how the test results will be protected against unauthorized disclosure. Include if the subjects are to be informed of the test results. If yes, include the process and provision for counseling. If no, a rationale for not informing the subjects should be included.

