#### Statistical Analysis Plan:

To assess the preliminary efficacy of the Activate program we will examine changes in proximal primary outcomes of average daily active minutes compared between treatment and control groups at baseline and the 12-week follow-up assessment. We will conduct multilevel models with baseline- residualized gain scores for outcomes to identify the effect size for the treatment program on each on the primary outcome. All participants will be used in analyses, with missing data addressed using an intention-to-treat approach where missing data were included and given a zero. A power sensitivity function was generated wherein our pilot study analyses were used to determine expected effect sizes. Anticipated effect sizes based on our pilot work for between group differences in behavior-change skills and average daily active minutes are Cohen's  $d$  of 0.4 to 1.2. With 60 participants, we will have 80% power to detect a Cohen's  $d$  of .7, 60% power to detect a Cohen's  $d$  of .6, at 95% power to detect a Cohen's  $d$  of .8. Thus, we will be powered to detect all but the smallest of potentially meaningful effects found in our previous intervention pilot work.

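### Power at d = 0.8 with 60 participants is 95% for Aim 1 and in the SAP but 90% for Aim 2, and the 95% does not fit the plan's own 60% and 80% at a 5% alpha

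*Protocol*

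**What the plan says.** Protocol, Statistical Considerations, Aim 1: with 60 participants there is 80% power at d = 0.7, and "60% power to detect a Cohen's d of .6, at 95% power to detect a Cohen's d of .8". The SAP carries the same statement ("With 60 participants, we will have 80% power to detect a Cohen's" d of 0.7), again with 60% at 0.6 and 95% at 0.8. Both expect pilot-based effects of d = 0.4 to 1.2.

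Protocol, Statistical Considerations, Aim 2: "with 60 participants, we will again have 80% power to detect a Cohen's d of .7, 60% power to detect a Cohen's d of .6", but then "at 90% power to detect a Cohen's d of .8". The expected range is narrower: "Based on our pilot work we anticipate effect sizes from Cohen's d of .4 to .8". The paragraph concludes: "We will be powered to detect all but the smallest of potentially meaningful effects found in our pilot work".

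The planned analysis is "multilevel models with baseline-residualized gain scores for outcomes", with the baseline outcome and disease covariates in the Aim 1 models. Neither document states alpha, sidedness, allocation ratio or assumed baseline correlation, or whether d is on the raw or the baseline-adjusted scale. The protocol section Inclusion of Children refers to this power section to justify 60 adolescents.

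**The concern.** One sample size and one pair of powers at d = 0.6 and 0.7 lead to two different powers at d = 0.8, and Aim 2 is worded as a restatement of the same function. A different outcome is no explanation, because Cohen's d already divides by the standard deviation. A different baseline correlation or number analysed would shift all three points, not only the last.

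The section is the plan's only justification for the sample size. As written, a reader cannot tell which figure applies or reproduce it, and the higher one is attached to the primary outcome. Aim 2's closing sentence also invites the reading that a null secondary result would be informative for most of the expected effects.

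**Working it through.** **Inputs.** From the documents: two arms, N = 60, stated powers 60/80/95% (Aim 1, SAP) and 60/80/90% (Aim 2) at d = 0.6/0.7/0.8. Assumed, because not stated: alpha 5%, two-sided (one-sided also tried); 1:1 allocation (20:40 to 30:30 also tried); all 60 analysed; baseline correlation r from 0 to about 0.94.

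**Step 1. Can the stated figures be reproduced?** Power is P(|T| > t*), where T is noncentral t with 58 df and noncentrality d·√(30·30/60) = d·√15 = 3.873d. The two-sided critical value is 2.002; the one-sided value is 1.672.

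| d | Noncentrality | Two-sided 5% | One-sided 5% | Aim 1 / SAP | Aim 2 |
|---|---|---|---|---|---|
| 0.4 | 1.549 | 33.2% | 45.5% | – | – |
| 0.6 | 2.324 | 62.8% | 74.3% | 60% | 60% |
| 0.7 | 2.711 | 76.0% | 85.0% | 80% | 80% |
| 0.8 | 3.098 | 86.1% | 92.2% | 95% | 90% |

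Two-sided, Aim 2's figures match after rounding to the nearest 10. The 95% does not: 95 − 86 = 9 points.

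**Step 2. Are the three points consistent with each other, whatever the design?** In the normal approximation, power = Φ(c·d − 1.96). N, allocation and r all enter only through c, so one stated point fixes the others at two-sided 5%.

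- From 80% at 0.7: c = (1.960 + 0.842)/0.7 = 4.002. Power is then 67% at 0.6 and 89% at 0.8.
- From 60% at 0.6: c = (1.960 + 0.253)/0.6 = 3.689. Power is then 73% at 0.7 and 84% at 0.8.
- From 95% at 0.8: c = (1.960 + 1.645)/0.8 = 4.506. Power is then 77% at 0.6 and 88% at 0.7, against the stated 60% and 80%.

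One-sided at 5%, calibrating to 95% at 0.8 gives 79% and 89%. Freeing alpha does not help: taking 60% and 80% literally needs a two-sided alpha near 0.001 and about 138 unadjusted participants, and still gives 92.4% at 0.8.

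**Step 3. What sample size does each stated point imply?** Noncentral t, two-sided 5%, 1:1, whole arms:

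| Stated point | n per arm | Total |
|---|---|---|
| 60% at 0.6 | 28.2 | 58 |
| 80% at 0.7 | 33.02 | 68 |
| 90% at 0.8 | 33.8 | 68 |
| 95% at 0.8 | 41.6 | 84 |

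So 95% at d = 0.8 needs 84 − 60 = 24 more participants than planned. With 60, power reaches 80% at d = 0.74, 90% at d = 0.85 and 95% at d = 0.95.

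**Step 4. Does baseline adjustment rescue 95%?** If d is on the raw scale, the effective effect is d/√(1 − r²), with 57 df. At r = 0.535 this gives 95% at 0.8, but 77% at 0.6 and 88% at 0.7. At r = 0.31 it gives 67/80/89%. Searching r and allocation for the smallest worst miss from 60/80/95, the best two-sided fit is 66/79/89% (r = 0.28, 30:30), 6.3 points off; the best one-sided fit is 9.8 points off. For 60/80/90 the best two-sided fit is 3.4 points off. If d is already on the adjusted scale, Step 1 applies unchanged.

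**Step 5. Aim 2's conclusion against its own numbers.** Power of 80% is claimed only from d = 0.7, which is (0.8 − 0.7)/(0.8 − 0.4) = 25% of the expected range. At 0.6, the middle of that range, the plan's own figure is 60%. For Aim 1 and the SAP the share is (1.2 − 0.7)/(1.2 − 0.4) = 62.5%, so there the sentence is loose and not contradictory.

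**The case against.** The stated powers are round numbers, and Aim 2's set is a fair rounded summary of 30 per arm at two-sided 5%. On that view the plan contains one wrong number, copied into the SAP. This stands, and it makes the 95% the outlier. It also tempers Step 3: solving for N from rounded powers gives false precision, and 33 per arm already yields 79.97% at d = 0.7. Only the 84 clearly stands apart.

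The one-sided best fit lies at the edge of the search (20:40, r = 0), so 9.8 points is not a true optimum. Step 2 does not depend on that search and reaches the same conclusion.

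The pilot effects are not shown, so the range alone does not say where they cluster or which were judged meaningful. Aim 2 is also exploratory and aims to estimate effect sizes. This limits the consequence, but the range and the 60% at d = 0.6 are all the plan offers in support of its closing sentence, and they do not support it.

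Finally, the plan sets no 95% target, so 84 is not a recruitment shortfall, and the conventional 80% point is only 4 points off. That is right: the error is in the stated power, not in a target that was missed.

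**Conclusion.** The point holds. The 5-point conflict at d = 0.8 is on the page and needs no assumption. That 95% cannot stand beside 60% and 80% rests on a 5% alpha, one- or two-sided, which the documents do not state; within that, neither allocation nor baseline correlation reconciles the three figures. Against 30 per arm, two-sided 5% and no covariate gain, the stated powers at d = 0.8 are 9 points (Aim 1, SAP) and 4 points (Aim 2) too high, and the 80% at d = 0.7 is 4 points too high. The Aim 2 figures are compatible with rounding; the 95% is not. Aim 2's closing sentence is not supported by its own numbers. As this is a preliminary-efficacy trial, the effect is confined to the justification of the sample size and the reading of imprecise results.

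**What to change.** State alpha, sidedness, allocation, the number expected in the analysis, any assumed baseline correlation, and the scale of d. Compute one power curve from these inputs and use it for Aims 1 and 2 and, for the primary outcome, in the SAP. Possible wording:

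> Assuming 30 analysed per arm, two-sided alpha 0.05, and d on the scale of the analysed outcome with no further covariate gain, power is 33%, 63%, 76% and 86% at d = 0.4, 0.6, 0.7 and 0.8; 80% power is reached at d = 0.74.

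If a baseline correlation is assumed, name it and recompute every point. Thirty per arm is the no-loss case. Withdrawal Procedures exclude withdrawn participants' data, whereas Statistical Considerations and the SAP include everyone, so the number analysed has to be settled first; with 25 per arm the powers at 0.6, 0.7 and 0.8 are 55%, 68% and 79%.

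Replace the closing sentence in Aim 2, and for consistency in Aim 1 and the SAP, with:

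> Effects below the 80%-power threshold (d = 0.74 under these assumptions) are not reliably detected and will be reported with confidence intervals.

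The cost is text only. Sample size and analyses do not change; the stated power becomes slightly less favourable.

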Data and Safety Monitoring Plan –As noted above, risks associated with this study are minimal and are not believed to exceed those adolescents already encounter in daily life. Specifically, the behavior change skills training and physical activity program is designed to help participants come closer to meeting the widely accepted guideline of engagement in at least one hour of moderate intensity physical activity each day (AHA and CDC^{61,62}). This level of involvement is believed necessary to yield optimal health benefits in persons with diabetes (ADA⁶⁴). Consequently, given the minimal risk nature of the protocol, the primary monitor of the data and participant safety will be Drs. [name]; this monitoring will occur on an ongoing basis, with the status of participant adolescents discussed at weekly meetings. Any adolescent experiencing difficulty with the physical activity program will be referred via the adolescent's parents to their physician for evaluation. The research team will document and review any adverse events that occur for each participant during the study. At baseline and 12-week follow up appointments, a research assistant will complete an adverse event form with the participant where they will be asked about any adverse events they have experienced over the past 3 months, in order to compare adverse events pre and post study, and between study conditions. Participants randomized to the intervention program will also have access to the adverse events form throughout the study period for additional reporting should they require it. We will also have an independent medical monitor review our summary of adverse event reports. Any adverse event will be reported to the local Institutional Review Board (IRB) in accordance with local guidelines. In addition, [name] will be responsible for assembling the study data and assisting in the preparation of annual data and safety monitoring reports. She will ensure that all monitoring plan personnel obtain copies of these reports in a timely fashion, prior to the deadline for each review. [name] will also oversee all communications with the Office of Research Protections to specifically include initial study approval; ongoing continuation reviews; and any necessary reporting of protocol deviations, protocol modifications, personnel changes, or adverse events.

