Should any adverse events, unanticipated problems or reportable new information arise, the PI will contact the IRB according to the Adverse Event and Unanticipated Problems Reporting Policy using the UVM Reporting Form.

Withdrawal Procedures: Define the precise criteria for withdrawing subjects from the study. Include a description of study requirements for when a subject withdraws him or herself from the study (if applicable).

At any time, a participant can choose to withdraw from participation. We do not anticipate withdrawing any adolescent from the study but reserve the right to do so under unforeseen circumstances. These might include situations such as discovery of a medical problem indicating the adolescent should not participate in physical activities. If a participant is withdrawn or withdraws from participation their data will not be included in analyses.

Sources of Materials: Identify sources of research material obtained from individually identifiable human subjects in the form of specimens, records or data. Indicate whether the material or data will be obtained specifically for research purposes or whether use will be made of existing specimens, records or data.

All data is being collected solely for research purposes. Participants will provide dried blood spot assays, measurements of abdominal circumference and blood pressure as well as complete computerized self-report questionnaires. This data will be coded at the time of collection.

DRUG INFORMATION

Investigators are encouraged to consult the UVM Medical Center Investigational Pharmacy Drug Service ([name]) prior to finalizing study drug/substance procedures.

Drug (s)

Not applicable

Drug name – generic followed by brand name and common abbreviations. Availability – Source and pharmacology; vial or product sizes and supplier. If a placebo will be used, identify its contents and source.

Preparation: Reconstitution instructions; preparation of a sterile product, compounded dosage form; mixing guidelines, including fluid and volume required. Identify who will prepare.

Storage and stability – for both intact and mixed products.

Administration – Describe acceptable routes and methods of administration and any associated risks of administration.

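### Adverse events are solicited on schedule only at baseline and week 12, with no exit assessment described, and the withdrawal rule drops leavers' data with no exception for safety, so the between-arm safety comparison is conditioned on completing the study

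*Protocol*

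**What the plan says.** All of the relevant text is in the protocol.

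- **Scheduled collection** (Data Safety and Monitoring, Data and Safety Monitoring Plan): "At baseline and 12-week follow up appointments, a research assistant will complete an adverse event form with the participant". The form's scope and purpose are given as follows: "any adverse events they have experienced over the past 3 months, in order to compare adverse events pre and post study, and between study conditions".
- **General commitment** (same section): "The research team will document and review any adverse events that occur for each participant during the study". On oversight it says: "this monitoring will occur on an ongoing basis, with the status of participant adolescents discussed at weekly meetings". An independent medical monitor reviews a summary of the adverse event reports, and events go to the IRB under local policy.
- **Between visits** (same section): "Participants randomized to the intervention program will also have access to the adverse events form throughout the study period for additional reporting". No equivalent is described for the control arm.
- **Withdrawal** (Withdrawal Procedures): investigator withdrawal is not expected, but the example given is "discovery of a medical problem indicating the adolescent should not participate in physical activities". The section ends: "If a participant is withdrawn or withdraws from participation their data will not be included in analyses". It describes no exit form, no exit call and no recording of the reason for leaving.

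Statistical Considerations and the SAP both say that every participant is analysed, but they do so for the outcome models. Neither mentions adverse events.

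**The concern.** The protocol promises a comparison of adverse events between conditions. The baseline form looks back over the period before randomisation, so the week-12 form is the only scheduled solicitation of events that occur on study. An adolescent who leaves before week 12 does not reach it. If an event in that adolescent became known by another route, the withdrawal rule as written would still keep it out of the analysis.

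Leaving may be related to safety. In an incentivised activity programme for adolescents with type 1 diabetes, a participant may stop because of overexertion, because of glucose problems around exercise, or because a contraindication comes to light. The first two are risks that the protocol itself names, and the third is close to its own example of a withdrawal. A comparison restricted to completers sets such events aside because of what happened after randomisation. With 60 participants in total, a few such cases could change how the result reads.

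**Working it through.** The documents contain no adverse event rate, dropout rate or safety power figure, so there is no stated figure to reproduce. The check is mainly a reading of the text, followed by an illustration of size.

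**Step 1. Follow three adolescents through the text.**

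| Participant | Scheduled on-study form | Other route by which an event may become known | Enters the between-arm comparison? |
|---|---|---|---|
| Attends week 12, either arm (even if activity has stopped) | Yes; the 3-month recall covers essentially the whole 12 weeks | General documentation; in Activate, also the between-visit form | Yes |
| Activate, leaves before week 12 | None described | General documentation; between-visit form, if the participant files it | No, under the withdrawal rule |
| Control, leaves before week 12 | None described | General documentation only | No, under the withdrawal rule |

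Two separate gaps follow. The first is in collection: nobody is scheduled to ask a leaver about events. The second is in analysis: whatever is known about a leaver is excluded. Closing one does not close the other.

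**Step 2. Size, for illustration only.** Assume 1:1 allocation, so 30 per arm (the protocol gives 60 in total and no ratio). In one arm let k leavers have had an event, let c completers have had an event, and let there be no other leavers.

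- Rate among all randomised: (c + k)/30
- Rate among completers: c/(30 − k)

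| c | k | All randomised | Completers only | Gap |
|---|---|---|---|---|
| 0 | 1 | 1/30 = 3.3% | 0/29 = 0% | 3.3 points |
| 3 | 1 | 4/30 = 13.3% | 3/29 = 10.3% | 3.0 points |
| 0 | 3 | 3/30 = 10.0% | 0/27 = 0% | 10.0 points |
| 3 | 3 | 6/30 = 20.0% | 3/27 = 11.1% | 8.9 points |
| 0 | 5 | 5/30 = 16.7% | 0/25 = 0% | 16.7 points |

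Each lost participant with an event is therefore about 3 percentage points of that arm's rate, and somewhat less when completers also have events.

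**Step 3. Direction.** Excluding leavers who had events lowers an arm's rate. Excluding leavers who had none raises it slightly: 3 events in 30, with 3 event-free leavers removed, becomes 3/27 = 11.1% instead of 10.0%. Leavers in the control arm act on the control rate in the same way. Separately, the between-visit form exists only in Activate and can raise the recorded count there. These forces oppose each other, and the documents give nothing with which to weigh them.

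**The case against.** A reader might infer that staff record adverse events only at the two appointments, so that a leaver has no follow-up safety record and the data are never collected. The documents do not support that. The sentence just before the one on the two appointments commits the team to documenting events for each participant during the study. Monitoring is ongoing, with weekly meetings. Activate participants can file the form at any time. The protocol's own example of withdrawal presupposes that the team has learned of the medical problem. Only the scheduled solicitation is confined to two visits.

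A reader might also infer that the medical monitor never sees leavers' events. The exclusion is from analyses. Nothing restricts the monitor's summary or the IRB reports to completers or to the two scheduled forms.

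A third tempting reading is that Activate will look safer than it is. It could, but its extra reporting route works the other way, and the medical problem in the example need not be an event caused by activity.

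It can also be said that this is a small trial described as minimal risk, that the adverse event comparison is neither a numbered aim nor part of the SAP, and that the attached intervention guide and the IRB policy, which are not available here, may say more about exits.

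These objections limit the point but do not remove it. The general commitment gives no method of asking leavers, the exclusion has no safety exception, and the protocol does state that the forms serve a between-condition comparison.

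**Conclusion.** The point holds in a limited form. As written, the between-arm adverse event comparison covers completers only. This follows from a stated rule and not merely from missing detail, because the exclusion applies even to leavers' events that the team has documented. Alongside it, no exit assessment is described, so leavers' events are not systematically sought in either arm.

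The size cannot be estimated from the documents. The figure of about 3 percentage points per lost participant with an event assumes 30 per arm, and the larger gaps in the table depend on hypothetical numbers of leavers. The net direction of bias is unknown. The conclusion rests on reading the withdrawal sentence literally and on the text available. Applying the statements that everyone is analysed to safety data would close the gap in analysis but would not create an exit assessment.

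**What to change.** 1. **Analysis.** In Withdrawal Procedures, state that the exclusion of withdrawn participants' data does not apply to safety data. In the Data and Safety Monitoring Plan, state that the between-condition comparison includes all adverse event data from every randomised participant, and that events leading to withdrawal are listed by arm.
2. **Collection.** At any withdrawal, in either arm, a research assistant completes the existing adverse event form by phone or video for the period since baseline and records the reason for leaving.

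The cost is a wording amendment and one short call per leaver, using the form and staff already in place. Some leavers will decline the call, so the number with no exit form should be reported by arm.
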